2. STUDY OBJECTIVES, ENDPOINTS

2.1 Study objectives

2.1.1 Primary objective and endpoint

The primary objective of the study is to assess the effectiveness of *Restylane Lyft Lidocaine* versus a no treatment control in Jawline definition by comparing Galderma Jawline Scale (GJS) response rates.

Primary Endpoint:

Responder rate based on the Blinded Evaluators' live assessment of the GJS at 3 months after last treatment for the Treatment group or after baseline for the No Treatment group.

A responder is defined as a subject with at least 1-point improvement from baseline, on both jawlines concurrently.

2.1.2 Secondary objective and endpoints

The secondary objective is to assess the effectiveness of *Restylane Lyft Lidocaine* for Jawline definition.

Secondary endpoints:

1. Responder rates based on the Blinded Evaluator's live assessment using the GJS at 6, 9 and 12 months after last treatment for the Treatment group or after baseline for the No Treatment group.

A responder is defined as a subject with at least 1-point improvement from baseline, on both jawlines concurrently, at each of the timepoints.

2. Proportion of subjects having at least "Improved" on the Global Aesthetic Improvement Scale (GAIS) on both jawlines concurrently, as assessed live by the Subject and Treating Investigator separately at 3, 6, 9 and 12 months after last treatment for the Treatment group and after baseline for the No Treatment group.

CONFIDENTIAL

One month is defined as 4 weeks in the study.

2.1.3 Safety objectives and endpoints

To evaluate the safety of *Restylane Lyft Lidocaine* by assessments of adverse events (AEs) by the Treating Investigator throughout the study period.

- Incidence, intensity, duration and onset of AEs collected during the study period post treatment.
- Pre-defined, expected, post-treatment events reported for 28 days from treatment as recorded in the subject diary.

2.2 Appropriateness of measurements

The effectiveness of *Restylane Lyft Lidocaine* for jawline definition will be evaluated by demonstrating superiority in responder rates (defined as at least 1 grade improvement from baseline on both jawlines concurrently on the GJS) relative to No Treatment group.

The GJS is a 5-point scale for assessment of jawline (see Section 6.3). Each score in the GJS is exemplified by Photographic images of the scale. The Blinded Evaluator and Treating Investigator will perform live assessment of the subject's left and right jawline separately.

The GJS was developed as a quantitative assessment of the jawline area in clinical trials. For the GJS to be considered a reliable and valid tool for assessing aesthetic improvements, live subjects were rated by an independent panel at two sessions separated at least two weeks apart in order to assess the intra- and inter-rater reliability. Based on the validation results, the GJS was determined to be fit for use in clinical settings to detect changes to treatment by improving the jawline definition as a result of volume correction.

Primary effectiveness of *Restylane Lyft Lidocaine* for jawline definition will be evaluated by comparing the responder rate based on the Blinded Evaluators' live assessment of the GJS at 3 months after last treatment. Secondary effectiveness of *Restylane Lyft Lidocaine* by comparing the responder rates based on the Blinded Evaluator's live assessment using the GJS at 6, 9 and 12 months after last treatment for the Treatment group or after baseline for the No Treatment group.

Secondary effectiveness measurements include GAIS as a widely used and accepted measure within the aesthetic field. Other secondary effectiveness measurements are the validated ^{CCI} as well as the ^{CCI} as well as the ^{CCI} as well as the ^{CCI} as secondary effectiveness are the validated ^{CCI} as well as the ^{CCI} as well as the ^{CCI} as well as the ^{CCI} as secondary effectiveness are the validated ^{CCI} as well as the ^{CCI} as a second the results.

Effectiveness evaluation in dermal filler clinical studies includes a combination of clinician-and subject-reported outcomes. As these are aesthetic devices and elective procedures, the incorporation of the subject perspective is critical to evaluate the study benefits associated with dermal fillers.

3. STUDY DESIGN

3.1 Overall design

This is a prospective, randomized, evaluator-blinded, no treatment controlled, parallel group, multicenter phase IV study to evaluate effectiveness and safety of *Restylane Lyft Lidocaine* for jawline definition. Approximately 140 subjects will be included in the study, randomized (3:1) to *Restylane Lyft Lidocaine* or to No Treatment (control) group.

Eligible subjects randomized to receive treatment will be injected by the Treating Investigator at Day 1. A follow-up telephone call should be made 72 hours after treatment.

Optional touch-up treatment may be administered 1 month (4 weeks) after initial treatment, if deemed necessary by Treating Investigator and the subject to obtain optimal aesthetic improvement. If optional touch-up is performed, a 72-hour follow-up telephone call and a follow-up visit after 1 month should be scheduled.

Effectiveness and safety data will be collected for up to 12 months after the last treatment for the Treatment group and after baseline for the No Treatment group including follow up visits at 1, 3, 6, 9 and 12 months.

Subjects in the No Treatment group will be offered optional treatment after 12 months (48 weeks) from baseline (Day 1) followed by a safety assessment 2 weeks after the optional treatment. Subjects who decline treatment after 12 months will end their study participation.

The treatment will be performed in accordance with approved Instructions for Use in Canada.

Investigator blinding will be accomplished by having a Treating Investigator administer the treatments and having a Blinded Evaluator, to whom randomization and treatment are concealed, conduct blinded assessments.

3.2 Study rationale and justification for design

The rationale of performing this study is to obtain further evidence of safety and effectiveness of *Restylane Lyft Lidocaine* for jawline definition in a randomized controlled trial. The intended use in this post-market study will be in accordance with the approved IFU. No treatment has been chosen as control as no treatment control is a commonly accepted comparator in aesthetic injectable filler trials.

A study of the safety and effectiveness of *Restylane Lyft Lidocaine* in the treatment of jawline will establish whether aesthetic jawline definition can be successfully achieved, with an acceptable safety profile.

By using a validated evaluation tool, the GJS assessed by the Blinded Evaluator and Investigator, the results of jawline definition reported can be confirmed by accurate measurements.

In addition, as established and used in other studies the GAIS and the validated ^{CCI}

will be used in this study and in addition a CCI as well as an CCI

3.3 Number of subjects and investigational centers

Approximately 140 subjects will be enrolled at approximately 10 study centers in Canada.

3.4 Study duration

The total duration of the study is estimated to approximately 18 months. This includes 4 months recruitment period.

- Treatment group:
 - Up to 21 days screening
 - \circ $\,$ Treatment at baseline (Day 1) and TC at 72 hrs after last treatment.
 - Optional touch-up at 1 month and TC at 72 hrs after last touch-up.
 - Data collection and safety follow-up visits at 1, 3, 6, 9 and 12 months after last treatment.
- No Treatment Control group:
 - Up to 21 days screening
 - Data collection and safety follow-up visits at 1, 3, 6, 9 and 12 months after baseline.
 - Optional treatment at 12 months after baseline followed by 2 weeks safety follow-up after optional treatment.

One month is defined as 4 weeks in the study.

3.5 Procedures/reasons for subject discontinuation

An investigator may decide to discontinue a subject from the clinical study for safety reasons.

Although the importance of completing the entire clinical study should be explained to the subject by the clinical study personnel, any subject is free to discontinue participation in this clinical study at any time and for whatever reason, specified or unspecified, and without any prejudice. No constraints are to be imposed on the subject, and when appropriate, a subject may be treated with other conventional therapy when clinically indicated.

When a subject does not complete the clinical study, he/she will be fully assessed if such assessment is possible. The procedures designated for the closest upcoming study visit should be completed for a subject discontinuing the clinical study and the appropriate electronic Case Report Form (eCRF) should be completed.

All discontinuations and the reason for discontinuation are to be documented by the investigator on the Study Exit form.

For discontinuation due to an AE, the Adverse Event form is to be completed. The investigator should also ensure that the subject receives suitable therapy for the AE.

A subject who has been randomized cannot be replaced by another subject if he/she discontinues the clinical study for any reason.

Pregnancies occurring during the screening period are considered as screening failures; they should be recorded as such in the eCRF and no pregnancy form is to be completed.

In case of a pregnancy occurring after the baseline visit, follow the procedures described in section 7.7.2. The subject may remain in the study, but no invasive procedure should be conducted.

The Sponsor may also decide to prematurely terminate or suspend a subject's participation in the clinical study.

Potential reasons for discontinuation are defined below:

The withdrawal criteria are:

- Medical Reasons If the subject suffers from a medical condition and/or Adverse Events that, in the judgment of the Investigator makes it medically necessary to withdraw the subject. The specific rationale for Investigator-initiated withdrawal of a subject for medical reasons should document the specific condition for withdrawing the subject.
- Withdrawal by Subject: Includes consent withdrawal, subject relocation, schedule conflicts. A subject can withdraw their consent to participate in the study at their own request or be withdrawn from participation in the study at the request of their legally authorized representative at any time for any reason.
- Lost to follow-up: If a subject does not return for a scheduled visit, reasonable effort shall be made to contact that subject, confirm with three documented phone calls and a certified letter (delivery receipt requested) without answer before declaring the subject lost to follow-up.
- Other: This category is to be used for a subject who discontinues due to a reason other than as specified in the pre-defined categories above. Explain the reason for discontinuation.

If reason for discontinuation is "withdrawal by subject" or "other", the subject will be questioned to rule out the possibility of an AE. If the AE led to discontinuation, then "Adverse Event" should be chosen as the reason for discontinuation, rather than "withdrawal by subject" or "other".

If an AE which, according to the Investigator's assessment, is related to the use of any of the study products and is still ongoing at the time of the withdrawal, the Investigator shall follow-up the subject until the AE resolves, is assessed by the Investigator to be "chronic" or "stable" or subject is lost to follow up. Follow-up information shall be reported on the AE follow-up form.

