7.7.2 Pregnancy

Pregnancy itself is not regarded as an AE.

If there is a pregnancy during the study period, the subject must be withdrawn from any following study treatment but should continue to be followed within the study and the outcome of pregnancy must be reported even if the delivery occurs after study completion.

A pregnancy confirmed during the study period must be reported by the Investigator on a pregnancy report form immediately upon acknowledge be submitted to the Sponsor according to contact details

specified in Section 7.7.1. The report can be prospective or retrospective. Follow-up shall be conducted to obtain outcome information on all prospective reports.

Cases that led to fetal distress, fetal death or a congenital abnormality or birth defect are to be regarded as SAEs and shall be reported on the exposure in utero report form to the Sponsor immediately but no later than 24 hours after the Investigators awareness. These events shall be handled as SAEs during data processing. Other complications during the pregnancy that are related to the pregnant woman and fulfils any serious criteria, such as pre-eclampsia requiring hospitalization, shall be reported and handled as SAEs. Elective abortions without complications shall not be reported as AEs.

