- Interview subject regarding the return to social engagements, where the Subject will be asked on when (in hours after treatment) the subject feels comfortable returning to social engagements (public/social appearances) exemplified as returning to business office or other public workplace, having dinner in a public restaurant, attending a social event/gathering such as dinner party, etc.
- Interview subject regarding the Diary completion and reported events since receiving treatment. Remind subject to complete the Diary daily and bring it to the next on-site visit.

• Remind subject of the next scheduled on-site visit.

8.3 Visit 3: Follow up visit 1 month (+ 7 days) after initial treatment / Optional touch-up or after baseline for the No Treatment group

- Interview subject regarding any concomitant therapies.
- Interview subject and evaluate any AEs that have occurred since the last visit.
- Obtain photographs (if treatment is given, ensure photos are taken prior to injection)

For subjects randomized to no treatment:

• Schedule Visit 4, 3 months (±7 days) after baseline visit).

For subjects randomized to treatment

- Collect and review Subject Diary:
 - Review diary entries for completeness and legibility.
 - If the subject handwrites entries on the diary pages, review these entries with the subject and clarify as needed. Record all clarifications on the subject's source documents and record the Diary data into the eCRF.
- Assess whether optimal aesthetic result has been achieved and determine whether optional touch-up is appropriate.
- Subject must meet eligibility criteria for touch-up to be provided.
 - Touch-up should not be provided if the subject has a disease or condition described in the exclusion criteria, or an ongoing treatment-related AE that in the opinion of the Treating Investigator would be worsened by a touch-up.
- Schedule Visit 4, 3 months (±7 days) after last treatment for subjects not receiving touchup.

If touch-up is to be performed:

- Prior to any treatment, perform UPT for all females of childbearing potential. The test result must be negative for a subject to receive the touch-up treatment.
- Prior to any treatment, assess GJS Treating Investigator.
- Subjects will be injected with the study product.
- Record all concomitant medications/procedures used prior, during or after the injection session.

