#### 2.4.2 Handling of Missing Data

Number of missing values will be summarized and reported as appropriate.

For the ITT analysis of the Blinded Evaluator GJS Responder rate at Month 3 after last treatment for Treatment group (primary endpoint), missing values will be assumed to be

	Title	Doc id
	05DF2209 Statistical Analysis Plan (SAP)	
GALDERMA		MA-58293
EST, 1981		WIA-30293

missing due to lack of effect. Therefore, the primary method of imputation will use the baseline observation carried forward (BOCF) method. Impact of missing data on the primary endpoint will be evaluated by performing sensitivity analysis based on the observed cases, as well as worst-case (No Treatment group imputed as responder, Treatment group imputed as non-responder) and best-case (Treatment group imputed as responder, No Treatment group imputed as non-responder) imputation in the ITT set.

All other effectiveness endpoints will be evaluated based on the observed cases in ITT.

Descriptive statistics of all safety data will be performed on observed cases in the Safety population.

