# 2.7 Determination of Sample Size

#### 2.7.1 Sample Size

A total sample size of approximately 140 subjects will be included in this study. For the responder rate in GJS, a Fisher's exact test using a 5% two-sided significance level will have approximately 90% power to demonstrate difference between a responder rate of 70% in the *Restylane Lyft Lidocaine* group, and a responder rate of 35% in the no treatment control group when the sample sizes are 105 and 35, respectively. Accounting for 10% dropouts, approximately 140 subjects need to be randomized in a 3:1 ratio.

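### Protocol 3.5 allows whole-study withdrawal for an AE or medical condition without providing for continued follow-up, so some subjects may lose the Month 3 score and will miss later visits; the effect is probably small and, for the primary endpoint, conservative

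*Protocol*

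**What the plan says.** Protocol 3.5 opens its rules on safety discontinuation with "An investigator may decide to discontinue a subject from the clinical study for safety reasons". Its list of withdrawal criteria includes medical reasons: a condition or AE that "in the judgment of the Investigator makes it medically necessary to withdraw the subject". Discontinuations go on the Study Exit form. A subject who leaves is to be fully assessed if possible, using the procedures of the closest upcoming visit.

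For pregnancy, 7.7.2 separates stopping treatment from leaving the study: "the subject must be withdrawn from any following study treatment but should continue to be followed within the study".

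For the touch-up, 8.3 says it should not be given when the subject has an exclusion condition or "an ongoing treatment-related AE that in the opinion of the Treating Investigator would be worsened by a touch-up". Study exit is not required. Section 8.5 has a parallel rule for the Month 12 optional treatment in the control group.

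On missing data, SAP 2.4.2 assumes that a missing Month 3 score reflects lack of effect, and so "the primary method of imputation will use the baseline observation carried forward (BOCF) method". Observed-case, worst-case and best-case sensitivity analyses are planned. For everything else, "All other effectiveness endpoints will be evaluated based on the observed cases in ITT".

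**The concern.** The intervention is one injection session on Day 1 and one optional touch-up a month later. After that, the treated arm receives no further product in the study. Rules for withholding the touch-up and the control group's Month 12 treatment already exist in 8.3 and 8.5. Taking a subject out of the study for an AE therefore adds little control over exposure; mainly it ends observation.

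Two kinds of data are at stake. At Month 3, a subject who still carries the implant and could have been rated may instead be set to non-response. The reason assumed for that (lack of effect) does not describe an investigator's withdrawal for an AE. At Months 6, 9 and 12 the subject leaves the observed-case denominators, and scheduled AE questioning stops. The protocol already has the needed distinction, in 7.7.2, but 3.5 does not use it for AEs and medical conditions.

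**Working it through.** **Step 1: the plan's own figure.** SAP 2.7.1 states that "a Fisher's exact test using a 5% two-sided significance level will have approximately 90% power" for 70% versus 35% with 105 and 35 subjects, and allows for 10% dropout with about 140 randomized 3:1.
- Exact two-sided Fisher power by full enumeration at 105/35, 70% versus 35%: 95.0%.
- At 94/31 (140 × 0.90 = 126, split about 3:1): 92.0%.
- Sample size by the two-proportion formula with continuity correction, 90% power, 3:1: 31 controls, 31 × 4 = 124 in total, 124/0.90 = 138 after rounding up. This agrees with about 140.

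So 140 reproduces if 105 and 35 are read as randomized numbers. The starting power for the next steps is 95.0%.

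**Step 2: when the Month 3 score is lost.** The exit assessment follows the closest upcoming visit, so Table 1 of the protocol decides what is captured in the treated arm.

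| Withdrawn | Next visit | Blinded Evaluator GJS at that visit? |
|---|---|---|
| After Day 1, before Visit 3 | 2a or 3 | No |
| After a touch-up, before Visit 3b | 3a or 3b | No |
| After Visit 3 without touch-up, or after Visit 3b | 4 (Month 3) | Yes |
| After Visit 4 | 5, 6 or 7 | Month 3 score already held |

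The loss falls on the first two rows, and on anyone in the third row who cannot be assessed. For the third row, the SAP does not say whether a GJS taken early at exit counts as the Month 3 value in the ITT analysis, hence "may lose" and not "loses".

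**Step 3: effect on the primary comparison.** Let w be the share withdrawn for medical reasons before Month 3 without a score and set to non-response. The documents give no value, so w is an assumption. If those withdrawn would have responded at the design rate, the expected treated rate is 0.70 × (1 − w). If the same share is lost and set to non-response among controls, their rate is 0.35 × (1 − w). Each treated subject lost lowers the treated rate by 0.70/105, or 0.67 percentage points, on average.

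| w | Treated rate | Power, loss in treated arm only | Power, equal loss in both arms |
|---|---|---|---|
| 0 | 70.0% | 95.0% | 95.0% |
| 1% | 69.3% | 94.1% | 94.6% |
| 2% | 68.6% | 93.1% | 94.1% |
| 5% | 66.5% | 89.4% | 92.4% |
| 10% | 63.0% | 80.0% | 88.8% |

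These are exact Fisher powers at 105/35 with no other missing data. The 10% row is a stress case. In 105 treated subjects, 1% to 5% is about 1 to 5 people.

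**Step 4: later visits.** If the true treated rate at a visit is p, a share w has been withdrawn and their own rate would have been r, the observed-case rate is (p − w × r)/(1 − w). As an illustration only, take p = 50% and w = 5%:
- r = 0: 0.50/0.95 = 52.6%
- r = 50%: (0.50 − 0.025)/0.95 = 50.0%
- r = 100%: (0.50 − 0.05)/0.95 = 47.4%

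The direction depends on how withdrawn subjects would have scored, which the documents do not tell us.

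**Step 5: safety follow-up after exit.** Related AEs still ongoing are followed until resolved, chronic, stable or lost to follow-up (3.5 and 7.4.5.1). Related AEs that start after the last visit are reported if the Investigator becomes aware of them, and followed until resolved (7.4.5.2). What ends is scheduled questioning and examination, and with it the collection of unrelated AEs and the active search for new ones.

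**The case against.** A reader might infer that 3.5 removes every subject with an AE from the study. It does not. Withdrawal is discretionary and limited to medical necessity, and staff are to explain the importance of completing the study. Under 8.3 a touch-up can be withheld and the subject goes on to Visit 4, so study exit is not the only tool available. Section 4.3.4 likewise has the Sponsor discuss how a subject who received a prohibited therapy may continue.

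A reader might also infer that the Month 3 score is always lost, that only ongoing related AEs are seen after exit, or that the loss is confined to the treated arm. Steps 2 and 5 rule out the first two. On the third, injection complications before Month 12 do arise only in treated subjects, but the criterion covers any medical condition, and those occur in both arms.

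On size, Protocol 1.3 anticipates few and transient AEs, and nothing in the documents supports a 5% medical withdrawal rate before Month 3. Even that rate in the treated arm alone leaves 89.4%, close to the planned 90%. Imputing non-response in the treated arm works against the product, sensitivity analyses are planned, and the later endpoints are outside formal testing.

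All of this stands and limits how often the problem arises and how much it matters. It does not close the gap: 3.5 still lacks the follow-up provision that 7.7.2 has, and the sensitivity analyses cannot recover scores or visits that never took place.

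**Conclusion.** The point holds in limited form. Section 3.5 permits whole-study withdrawal for an AE or medical condition and does not provide for continued follow-up. Some early exits may therefore become imputed non-responders at Month 3, and every such exit forgoes the remaining scheduled effectiveness and AE visits.

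The effect is probably small and conservative for the primary endpoint. Under an assumed loss of 1% to 5% before Month 3, power falls from 95.0% to 94.1–89.4% if only the treated arm is affected, and to 94.6–92.4% if both arms are affected equally. These figures rest on the design rates, 105/35, non-response imputed for each loss and no other missing data. For Months 6 to 12 the documents support no figure, only the possibility of bias if withdrawn subjects would have scored differently from those who stayed. They do not support a claim that the primary result is put at risk or that the product is favoured there. The case for change is that it keeps obtainable data at very little cost.

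**What to change.** Amend Protocol 3.5 and reconcile it with 7.7.2, 8.3 and 8.5. State that a medical or AE reason does not by itself end scheduled follow-up. Unless the subject withdraws consent or is lost to follow-up, the scheduled visits, Blinded Evaluator GJS, GAIS and AE collection continue. Decisions on injection stay where the documents already place them; the amendment should add no rule on treatment.

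The SAP needs no new rule for this. BOCF applies only to missing values, so scores obtained at Month 3 enter the ITT analysis under 2.4.2 as written.

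The cost is one paragraph in a protocol amendment. The visits are already in the schedule, so none are added. The downside is that sites keep seeing a few subjects they might otherwise have exited.
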